Are there differences in the activation of brain areas with positive and negative emotional stimuli that are related to the degree of emotional disorder that can be used in symptomatic patients to develop personalized treatment strategies?

GENERAL AND SPECIFIC OBJECTIVE

The general objective is to demonstrate the relationship between the activation of brain areas and its intensity with the degree of emotional disturbance. In turn, the recognized patterns will be compared with the different degrees of emotional disorder determined by a validated survey, to try to determine the weight of the emotional disorder on each type of activation according to the stimulus received as a specific objective on each one of them in particular.

HYPOTHESIS

The activation of specific brain areas follows common patterns for basic emotions and their derived feelings depending on whether they are positive or negative emotions, while in patients with emotional deficits the activation patterns are different and this difference can manifest itself in specific emotions.

METHODOLOGY TYPE OF STUDY

Initial exploratory, observational, cross-sectional study.

UNIVERSE

Population of the City of La Rioja.

SAMPLE

We estimate that 13 participants would give the study more than 80% power to detect a change between measures of 5% or more, using a linear mixed model for repeated measures, with a type I error of 5% (3).

INCLUSION, EXCLUSION AND ELIMINATION CRITERIA

Volunteers who express their informed consent to participate in the research protocol will be included. The exclusion criteria will be the impossibility of the patient to actively collaborate with the tests to be carried out for the measurement of emotional responses and / or the conditions that represent contraindications for carrying out MRI studies in general. The elimination criterion will be the appearance of any of the two exclusion criteria mentioned at any time during the development of the research.

OPERATIONALIZATION OF VARIABLES

Variable: increased metabolism of a brain area before the application of an emotional stimulus. The stimuli will be generated by paradigms designed to generate positive and negative emotional responses, using audiovisual material constituted by fragments of films validated for the local population (9), following in all cases the quality requirements of paradigms defined by the American Society of Functional Neuroradiology (ASFNR).

Type of variable: dependent, controlled.

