The final data processing will be carried out with statistical tools to quantitatively compare the activation areas in the different clinical scenarios according to the type of stimulus administered. The activation areas before the positive and negative stimulus will be quantified in cm³ and fMRI Z-score and correlated with the score of the emotional questionnaire. Pierson's correlation coefficient will be used for data of normal distribution or Spearman in case of not having normal distribution.

PLAN FOR THE PRESENTATION OF THE INFORMATION

Starting on July 1, 2021, it is planned to provide the Committee with information on the progress of the project every 30 days, namely on 8/1, 9/1, 10/1 and 11/1, 2021 to later present the final report.

SCHEDULE OF ACTIVITIES

Calibration and fine-tuning of the enabled software and tests in healthy volunteers of the auditory and visual paradigms developed by the researchers. From 7/1/21 to 7/25/21. fMRI sessions for the quantification of emotions in different parameters with healthy volunteers. From 7/28/21 to 10/30/21.

Statistical post-processing of results from 11/01/21 to 11/22/21. Presentation of the final report on 11/30/21 and subsequent submission to a scientific journal for consideration of its publication.

BUDGET

The use of the BOLD sequence to perform fMRI is provided free of charge by Philips for a limited period of time for the purposes of carrying out this research protocol. No disposables or medications are used. The necessary elements for the construction of paradigms, stationery, etc. they will be contributed by the researchers. No expenses are generated for

Incor, except for the use of the room, light, etc., during the MRI acquisitions that will be carried out at specific times without interfering with the healthcare task.

ETHICAL CONSIDERATIONS

The informed consent of each volunteer participant will be requested, including a personal interview to clarify any doubts that may arise and explain in detail and clearly the characteristics of the study. Attached is a letter of adherence to the 2013 Declaration of Helsinki. The researcher's Certificate of Ethics issued by the La Rioja Council of Physicians is attached. The protocol is presented for evaluation by INCOR's Ethics Committee.

BIBLIOGRAPHY

1-Ríos, M. Neurosychology and Functional Magnetic Resonance. Radiology. Volume 50, Issue 5, October 2008 , , pages 351-365. doi: 10.1016 / S0033-8338 (08) 76050-8

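### Schedule, eligibility criteria and hypothesis describe different populations, so the hypothesis clause about patients with emotional deficits is not secured

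*Protocol*

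**What the plan says.** Three parts of the protocol state who is studied.

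- **Schedule of Activities.** The measurement phase, 7/28/21 to 10/30/21, is described as "fMRI sessions for the quantification of emotions in different parameters with healthy volunteers". Calibration has its own line and dates (7/1/21 to 7/25/21) and also names healthy volunteers. No other session is listed.
- **Hypothesis.** Basic emotions follow common activation patterns, "while in patients with emotional deficits the activation patterns are different". The Research Question looks for differences "that can be used in symptomatic patients to develop personalized treatment strategies".
- **Inclusion, Exclusion and Elimination Criteria.** "Volunteers who express their informed consent to participate in the research protocol will be included". The two exclusions are inability to cooperate with the tests and contraindications to MRI. The Universe is "Population of the City of La Rioja".

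Two further sections affect how these are read. Under General and Specific Objective, activation patterns are to be "compared with the different degrees of emotional disorder determined by a validated survey". The Statistical Analysis Program correlates activation, in cm³ and as a Z-score, with the questionnaire score.

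**The concern.** The hypothesis makes a statement about affected people, the schedule describes the people scanned as healthy, and the eligibility criteria are silent on the matter. If the hypothesis is reported as confirmed or refuted, a reader cannot tell from the protocol whether anyone with an emotional deficit contributed data.

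This matters because the Justification and the Research Question look ahead to treatment strategies for symptomatic patients. That inference needs either affected participants or a score range that reaches into the affected region. The protocol secures neither. Who is scanned, who is eligible and what is hypothesised are all protocol content, so this is not detail that can be left to a statistical analysis plan.

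**Working it through.** The point rests on a comparison of the text. The one design figure, the sample size, does not settle it.

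**Step 1: is the schedule line left over from piloting?** No. Calibration (7/1/21 to 7/25/21) and measurement (7/28/21 to 10/30/21) are separate entries with dates that do not overlap, and both name healthy volunteers.

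**Step 2: do the eligibility criteria resolve it?**

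| Section | Requires health? | Requires or secures emotional deficit? |
|---|---|---|
| Schedule, measurement phase | Says healthy, undefined | No |
| Inclusion (consent) | No | No |
| Exclusions (cooperation, MRI safety) | No, apart from these two conditions | No |
| Hypothesis, second clause | No | Presupposes such patients, undefined |

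The criteria agree with neither of the other two sections. They allow affected people to enter but reserve no place for them.

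**Step 3: does the questionnaire define the groups?** Operationalization of Variables grades volunteers by CESIM-37 score. It gives no score that marks an emotional deficit, no score that marks health, and no strata or quota.

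**Step 4: does the sample size help?** The Sample section says "We estimate that 13 participants would give the study more than 80% power" for a change between measures of 5% or more. That is a within-person quantity. It allocates none of the 13 to an affected group. It also cannot be reproduced, since no standard deviation or within-person correlation is given, so nothing here relies on it.

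**Step 5: what follows under each reading?**

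- *Healthy is a real screen.* Some affected people would be kept out, to an unknown extent, and the CESIM range would be narrowed to an unknown degree. The patient clause is not secured.
- *Healthy is only a loose label and eligibility governs.* Affected people may volunteer, but nothing ensures that they do. The patient clause is again not secured.
- *Under both,* the correlation of activation with CESIM-37 score can be computed, and it describes only the scores observed.

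**Step 6: timing.** The protocol is marked as updated 10/11/2021. Read as month/day, that falls inside the scheduled measurement window. Read as day/month, it falls after the window closes on 10/30/21. Either way, a further change to the hypothesis may come after data exist. The protocol does not say how many scans had been done.

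**The case against.** The strongest defence is that this is a graded design and not a comparison of two groups. The general objective concerns degree of disturbance, everyone completes the CESIM-37 before imaging, and the only analysis of disorder is a correlation. The protocol also uses the word patient for any participant, as in "The exclusion criteria will be the impossibility of the patient to actively collaborate with the tests". On that reading, patients with emotional deficits may simply mean higher-scoring volunteers, and healthy may mean without a known diagnosis. The study is also labelled initial and exploratory.

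Much of this stands. The planned analysis does not depend on a separate patient group, and the text does not support three stronger readings that a reader might infer:

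- *That no affected person would be scanned.* The word healthy is undefined and no screen or cut-off is stated, so a count of zero cannot be derived.
- *That the study can test nothing about emotional disorder.* The correlation remains estimable under every reading.
- *That a probability of recruiting no affected person, or a loss of power from a restricted score range, can be attached.* Such figures would need an assumed prevalence of a status that the protocol never defines, a random draw from what is a volunteer sample, and an assumed correlation and score distribution. None of these is in the document.

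The defence does not rescue the patient clause. Grading by score identifies people with deficits only if some score is said to mark them, and none is. Being exploratory lowers the standard of proof, but it does not settle which population was studied.

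**Conclusion.** The point holds as an inconsistency that limits what may be concluded. The measurement-phase line, the eligibility criteria and the second clause of the hypothesis do not describe one population, and no section reconciles them. As written, the plan cannot be relied on to support the patient clause or an inference to symptomatic patients. It can support a statement about activation and CESIM-37 score over the range recruited.

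The severity is minor to should-fix. Confidence is high for the mismatch in the text. The size of the consequence is unknown, because it depends on how healthy was applied and on the scores obtained. The conclusion rests on no assumed prevalence, correlation or power.

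**What to change.** Make the schedule, eligibility criteria and hypothesis describe the same population, and let it be the one actually scanned.

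- **If no health screen is applied:** delete the word healthy from the measurement-phase line. State the hypothesis as: activation (cm³ and Z-score) under positive and negative stimuli is associated with CESIM-37 score.
- **If a health screen is applied:** define it in the inclusion criteria, and restrict both hypothesis and conclusions to healthy volunteers.

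In both cases:

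- drop the patient-group claim;
- report the observed CESIM minimum, maximum and SD beside each correlation, and limit conclusions to that range;
- date any change of hypothesis wording relative to scanning, and label it post hoc if data had already been collected.

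The choice must follow what was done. Removing the word healthy after a screen had been used would misdescribe the sample.

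The cost is a short text amendment, with no extra scans and no change to the measurements or the correlation. The downside is a narrower, graded claim with no patient-group effect. The first option does not itself guarantee a wide spread of scores, which is why the observed range has to be reported.
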